5. TREATMENT OF SUBJECTS

5.1. Drugs Administered During the Study

5.1.1. Pridopidine

In this study, pridopidine can be administered as 0.5 or 1 mg in healthy subjects (Part A only); 2.5, 5, 10, 22.5, 45, 67.5, or 90 mg in healthy subjects and HD patients; and a higher dose of 112.5 mg may also be administered to HD patients. The applicable dose will be given selecting the lowest possible number of capsules. Pridopidine will be administered orally with 240 mL of water.

Study drug will be packaged in bottles and will be provided to the site for administration to subjects (see Section 3.9).

Lower dose study drugs will be packed in bottles on site (1 bottle per patient), prior to administration to the subjects.

5.1.2. [¹⁸F]fluspidine

The radiolabeled PET tracer [¹⁸F]fluspidine will be provided as a sterile, clear, colorless particle free solution to be administered intravenously for the neuroimaging of S1R brain receptors. The label on the tracer delivered for use in the PET scans will contain information regarding the composition of the product.

During the study period, the subjects will undergo a baseline PET investigation (PET session 1) and a post-treatment PET investigation during the study period (PET session 2) following a single oral dose of the study drug, pridopidine. On the day of each PET session, prior to PET imaging, a cubital or forearm vein will be cannulated to inject (S)-(-)-[¹⁸F]fluspidine (300±30 MBq) and, at visit 3, to obtain venous blood samples for quantification of pridopidine and its metabolite TV-45065 and other exploratory biomarker analysis. The subject's radial artery on the other arm (or the same arm if this cannot be achieved) will be cannulated to obtain arterial blood samples during PET imaging for the quantification of plasma radioactivity associated with (S)-(-)-[¹⁸F]fluspidine, in order to estimate a metabolite-corrected arterial plasma input function for PET data analysis. A total of 51 samples (43 × 2 mL and 8 × 10 mL) will be collected at 39 time points during 210 minutes after injection of the tracer. The arterial sampling intervals will be according to the institutional standards, as detailed in the study imaging manual.

If any of the postdose PET investigations are compromised due to technical or logistic reasons, a repeat investigation may be considered, provided that the resulting cumulative (S)-(-)-[¹⁸F]fluspidine dose for all PET sessions does not exceed the authorized overall study exposure (effective dose not exceeding 20 mSv), when using tracer administered activity of 300±30 MBq per PET session, and further respecting a washout of 7 days of pridopidine and its metabolites.

5.1.3. [¹⁸F]fallypride

The radiolabeled PET tracer [¹⁸F]fallypride will be provided as a sterile clear colorless particle free solution to be administered intravenously for the neuroimaging of D2 receptors in the brain.

The label on the tracer delivered for use in the PET scans will contain information regarding the composition of the product.

During the study period, the subjects will undergo a baseline PET investigation (PET session 1) and a post-treatment PET investigation during the study period (PET session 2) following a single oral dose of the study drug, pridopidine. On the day of each PET session, prior to PET imaging, a cubital or forearm vein will be cannulated to inject [¹⁸F]fallypride (200±20 MBq) and, at visit 3, to obtain venous blood samples for quantification of pridopidine and its metabolite TV-45065 and other exploratory biomarker analysis.

If any of the postdose PET investigations are compromised due to technical or logistic reasons, a repeat investigation may be considered, provided that the resulting cumulative [¹⁸F]fallypride dose for all PET sessions does not exceed the authorized overall study exposure (effective dose not exceeding 20 mSv), when using tracer administered activity of 200±20 MBq per PET session, and further respecting a washout of 7 days of pridopidine and its metabolites.

5.2. Restrictions

Medications prohibited before and/or during the study are described in Section 5.3. Restrictions in regard to birth control and required laboratory values are provided in the inclusion and exclusion criteria.

Healthy subjects will be required to comply with the following additional restrictions:

- Activity
 - Subjects must remain seated or supine for safety reasons during the pridopidine administration and for 1 hour after each pridopidine administration. Subjects will be allowed to use the restroom (escorted by investigational center staff) during this time, as needed.
 - Subjects will be asked to maintain normal physical activity from at least 5 days before the start of the study.
 - Subjects are not to engage in strenuous exercise during the inpatient periods of this study.
- Fasting
 - Subjects will fast from waking; a light breakfast (without caffeine) is allowed, to be completed at least 2 hours before drug administration.
- Specific food, beverages, etc
 - Subjects may not consume any food or drink/beverage containing alcohol, grapefruit or grapefruit juice, apple or orange juice, vegetables from the mustard green family (eg, kale, broccoli, watercress, collard greens, kohlrabi, brussel sprouts, mustard), and charbroiled meats within 7 days before the first day of study drug administration until after the last day of pharmacokinetic sampling.
 - Daily consumption of more than 6 units of caffeine and/or xanthine-containing products will be prohibited for a minimum of 2 weeks before the first dose of study drug. One caffeine unit is contained in the following items: 1 cup of coffee,

2 cans of cola, 1 cup of tea, $\frac{1}{2}$ cup of energy drink (eg, Red Bull), or 3 chocolate bars. Consumption of such products will be restricted to no more than 2 units of caffeine-containing foods or drinks from 48 hours prior to admission visit and discharge. Subject should be able to abstain from caffeine intake for 20 hours during any day. Caffeine must not be consumed after 1800 hours on day -1 at visits 2 and 3, and should not be provided with breakfast on day 1 of visits 2 and 3.

- Subjects must not donate any blood products (eg, plasma, platelets, etc) during the study or during the 1 month after the last study visit.
- Smoking >5 cigarettes per week is not permitted during the study.

Patients will be required to comply with the following additional restrictions to the best of their ability:

- Activity
 - Patients must remain seated or supine for safety reasons during the pridopidine administration and for 1 hour after each pridopidine administration. Patients will be allowed to use the restroom (escorted by investigational center staff) during this time, as needed.
- Fasting
 - Patients will fast from waking; a light breakfast (without caffeine) is allowed, to be completed at least 2 hours before drug administration.
- Specific food, beverages, etc
 - Patients may not consume any food or drink/beverage containing alcohol, grapefruit or grapefruit juice, apple or orange juice, vegetables from the mustard green family (eg, kale, broccoli, watercress, collard greens, kohlrabi, brussel sprouts, mustard), and charbroiled meats within 7 days before the first day of study drug administration until after the last day of pharmacokinetic sampling.
 - Caffeine must not be consumed after 1800 hours on day -1 at visits 2 and 3, and should not be provided with breakfast on day 1 of visits 2 and 3.
- Patients must not donate any blood products (eg, plasma, platelets, etc) during the study or during the 1 month after the last study visit.

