3.2. Justification for Study Design

The number of subjects studied per dose group is expected to be sufficient to meet the study objectives, which are not based on formal statistical hypothesis. Each dose-group will comprise up to 4 subjects (deviations will be allowed). An additional subject will be added if the results from 1 out of 3 subjects are discordant. It is anticipated that 3 dose levels will be sufficient to characterize the exposure-response profile (deviations will be allowed). However, additional cohorts may be studied. A cohort of HD patients may be added to study engagement of pridopidine to S1R and 2D receptors and to explore the effects of neurodegeneration in patients with HD.

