- a positive urine drug test or a positive alcohol breath analyzer test at admission visits, or not willing or able to refrain from illicit drugs during the study.

v. Donation or reception of any blood products (eg, plasma, platelets, etc) in the 1 month before the first day of study drug administration, or has made more than 2 donations within the 12 months preceding the first day of study drug administration, or plans to donate during the study or during the 1 months after the last study visit.

w. The subjects cannot participate or successfully complete the study, in the opinion of the investigator, for any of the following reasons:

- The subject is mentally or legally incapacitated, or unable to give consent for any reason.
- The subject is in custody due to an administrative or a legal decision, or under tutelage, or being admitted to a sanitarium or social institution.
- The subject is unable to be contacted in case of emergency.
- The subject is an employee of the site or a relative of an employee at the site.
- Any other reason, at the discretion of the investigator.

Patients with Huntington's disease:

- a. CYP2D6 poor metabolizers
- b. The patient has been previously exposed to ionizing radiation or radioactive substances as a result of clinical research or medical treatment in the past 10 years.
- c. The patient has large scale tattoos, in particular involving the head and neck area.
- d. The patient has a counterindication to having an MRI, including (but not limited to):
 - The presence of metal implants (excluding metal dental crowns) that could affect MRI imaging OR
 - has worked with ferrous metals either as a vocation or hobby (for example sheet metal worker, welder or machinist) in such a way that might have led to unknown indwelling of metal fragments that could cause injury if moved in response to the magnetic fields during the MRI imaging.
- e. The patient suffers from claustrophobia or needle phobia.
- f. The patient has a finding on screening MRI that will, in the opinion of the PI impair the safety of the subject or the scientific integrity of the study.
- g. The patient has a severe motor impairment that might cause artifacts.
- h. The patient has an known coagulation abnormality.
- i. Parts A and 0 only: Individuals who had evidence of only one patent arterial supply to the hand (modified Allen test).

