- any food or drink/beverage containing alcohol, grapefruit or grapefruit juice, apple or orange juice, vegetables from the mustard green family (eg, kale, broccoli, watercress, collard greens, kohlrabi, brussel sprouts, mustard), and charbroiled meats within 7 days before the first day of study drug administration until after the last day of pharmacokinetic sampling.
- a positive urine drug test or positive alcohol breath analyzer test at admission visits, or not willing or able to refrain from illicit drugs during the study.

aa. Positive serology for HIV-1, HIV-2, HBsAg, and/or hepatitis C.

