5.5. Total Blood Volume

The total blood volume to be collected for each subject in this study is approximately 436.9 mL for Part 0 ([Table 2](#), see table footnote), 467.8 mL for Part A ([Table 2](#)), 499.6 mL for Part A (0.5 and 1 mg only [[Table 3](#)]), and approximately 135.8 mL for Part B ([Table 4](#)), where arterial sampling will not be performed.

Table 2: Blood Volumes (Part 0 and Part A)

Type of samples	Volume per sample (mL)	Total number of samples	Total volume (mL)
Serum chemistry	4.7	4	18.8
Hematology	2.7	4	10.8
Coagulation	2.7	1	2.7
Virology	4.7	1	4.7
Corticoid	4.7	2	9.4
Arterial (1)	2	86	172
Arterial (2)	10	16	160
Pharmacokinetic ^a	2	16	32
Pharmacogenetic	4.9	1	4.9
Biomarkers	10.5	5	52.5
Total			467.8

^a Not applicable for Part 0, where total blood volume will be approximately 436.9 mL.

Table 3: Blood Volumes (Part A [Dose Cohorts 0.5 and 1 mg Only])

Type of samples	Volume per sample (mL)	Total number of samples	Total volume (mL)
Serum chemistry	4.7	4	18.8
Hematology	2.7	4	10.8
Coagulation	2.7	1	2.7
Virology	4.7	1	4.7
Corticoid	4.7	2	9.4
Arterial (1)	2	86	172
Arterial (2)	10	16	160
Pharmacokinetic	6	16	96
Pharmacogenetic	2.7	1	2.7
Biomarkers	4.5	5	22.5
Total			499.6

Table 4: Blood Volumes (Part B)

Type of samples	Volume per sample (mL)	Total number of samples	Total volume (mL)
Serum chemistry	4.7	4	18.8
Hematology	2.7	4	10.8
Coagulation	2.7	1	2.7
Virology	4.7	1	4.7
Corticoid	4.7	2	9.4
Pharmacokinetic	2	16	32
Pharmacogenetic	4.9	1	4.9
Biomarkers	10.5	5	52.5
Total			135.8

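### The healthy-subject exclusion for recent blood donation has no counterpart in the HD exclusion list, although HD patients may enter Part A and give the same 467.8 mL (minor)

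*Protocol*

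**What the plan says.** For healthy subjects, criterion v of Protocol Section 4.2 excludes "Donation or reception of any blood products (eg, plasma, platelets, etc) in the 1 month before the first day of study drug administration", and also anyone who "has made more than 2 donations within the 12 months preceding the first day of study drug administration". It excludes those who plan to donate during or shortly after the study as well. The synopsis carries the same criterion.

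The HD exclusion list in Section 4.2 runs from a to aa and ends with "Positive serology for HIV-1, HIV-2, HBsAg, and/or hepatitis C". None of its items mentions donation, and neither do the HD inclusion criteria in Section 4.1. The synopsis lists agree with this.

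The one donation rule for HD patients is a bullet in Section 5.2: "Patients must not donate any blood products (eg, plasma, platelets, etc) during the study or during the 1 month after the last study visit". The healthy-subject bullet in the same section has the same content. The lead-in differs: HD patients are asked to follow their restrictions as far as they are able.

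Section 5.5 sets the sampling volumes by part, without separating the populations: "The total blood volume to be collected for each subject in this study is approximately" 467.8 mL for Part A (Table 2), 499.6 mL for the 0.5 and 1 mg cohorts of Part A (Table 3), and 135.8 mL for Part B (Table 4). The SAP has no eligibility or sampling-volume text that would fill the gap.

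**The concern.** Criterion v keeps a healthy volunteer from adding the study's blood loss to a recent donation. HD patients assigned to Part A have the same arterial and venous sampling, yet nothing in their eligibility criteria asks about donation. A recent HD donor with unremarkable screening laboratory results meets no exclusion criterion. The healthy list also ends with a general clause (criterion w) that lets the investigator exclude for any reason, and the HD list has no such clause.

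What is at stake is a small safety margin on blood loss, and the consistency of two lists that the same protocol applies to the same procedure. No estimate or test in the study depends on it.

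**Working it through.** **1. Can an HD patient be in Part A, and which volume applies?** Yes. The primary objective in Section 2.2.1 covers S1R occupancy in (optional) HD patients. Section 3.2 says "A cohort of HD patients may be added to study engagement of pridopidine to S1R and 2D receptors". HD exclusion i is an arterial-supply criterion limited to Parts A and 0. HD doses begin at 2.5 mg (Section 5.1.1: "2.5, 5, 10, 22.5, 45, 67.5, or 90 mg in healthy subjects and HD patients"), so Table 2 applies and not Table 3.

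**2. Reproduce the plan's figure.** Table 2, volume per sample × number of samples:

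18.8 + 10.8 + 2.7 + 4.7 + 9.4 + 172 + 160 + 32 + 4.9 + 52.5 = **467.8 mL**, as stated.

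Arterial check against Section 5.1.2: 43 × 2 + 8 × 10 = 166 mL per session; 2 × 166 = **332 mL** = 172 + 160.

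**3. Spread over visits** (Table 1 and Sections 3.14.1 to 3.14.4):

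| Visit | Components (mL) | Total (mL) |
|---|---|---|
| Screening | 4.7 + 2.7 + 2.7 + 4.7 + 4.9 | 19.7 |
| Visit 2 | 4.7 + 2.7 + 4.7 + 166 | 178.1 |
| Visit 3 | 4.7 + 2.7 + 4.7 + 166 + 32 + 52.5 | 262.6 |
| Follow-up | 4.7 + 2.7 | 7.4 |
| Sum | | 467.8 |

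**4. Share of blood volume.** Weight 50 kg is the HD inclusion minimum. Blood volume of 70 mL/kg is my assumption, giving 50 × 70 = 3,500 mL.

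- Visit 2: 178.1 / 3,500 = 5.1%
- Visit 3: 262.6 / 3,500 = 7.5%
- Whole study: 467.8 / 3,500 = 13.4%
- Part B instead: 135.8 / 3,500 = 3.9%

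**5. How much of the month before dosing is open for HD patients?** Screening takes place 2 to 8 weeks before visit 2 (Section 3.14.1). Suppose the Section 5.2 ban starts at consent, and take a month as 30 days (assumption). Uncovered days = max(0, 30 − days from consent to first study drug).

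- Shortest screening, counting the visit 2 tracer as first study drug: 30 − 14 = 16 days
- The same, counting from pridopidine at visit 3: fewer than 16 days
- Eight-week screening: 30 − 56 < 0, so nil

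If the ban started only at the first admission, essentially the whole month would be open. The 12-month count is missing on every reading.

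**6. Upper bound with a donation.** Assume a donation of 450 to 500 mL and no replacement:

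- 50 kg: (467.8 + 450) / 3,500 = 26.2% to (467.8 + 500) / 3,500 = 27.7%
- 75 kg (5,250 mL): 917.8 / 5,250 = 17.5% to 967.8 / 5,250 = 18.4%

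**The case against.** The strongest reply is that little risk remains.

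- **The restriction probably starts early.** Section 3.11 counts screening in the duration of participation, and subjects are told the restrictions at screening (Table 1, footnote a). On that reading a donation must precede visit 2 by at least 2 weeks. This stands, although the protocol does not define when the period starts, and for HD patients the restriction is best-effort.
- **Other checks exist.** Hematology, including hemoglobin and hematocrit, is done at screening and on day -1 of visits 2 and 3. Medical history is reviewed twice. Procedures in the 28 days before study drug are recorded (Section 5.3). HD criteria n and s allow exclusion on medical grounds, and the investigator may withdraw anyone (Section 3.12). These reduce the risk, but none makes a recent donation a reason not to enrol.
- **The lists differ on purpose elsewhere.** Creatinine clearance limits are 90 and 60 mL/min, and Section 4.3 describes its criteria as the usual ones for healthy subjects. That explains differences in general, but the readable text does not explain this one. Parts of Section 4.3 are redacted.
- **Exposure is small.** The HD cohort is optional, up to 4 patients, and Section 9.1 links it to D2R, which would mean Part B and 135.8 mL. This stands and limits the severity.

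A reader might infer two further defects that the documents do not support. First, that Section 5.2 treats HD patients differently: its two donation bullets match. Second, that HD patients lack a comparable hemoglobin safeguard: healthy criterion k also needs the investigator to judge the low value clinically significant, so it works much like HD criterion s.

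**Conclusion.** The asymmetry is real and confined to the exclusion lists in Section 4.2 and the synopsis. Healthy subjects have a 1-month and a 12-month donation limit before study drug, and HD patients have neither. With the Section 5.2 ban read as starting at consent, the 1-month gap is about 2 weeks at most and may vanish with long screening. The 12-month gap remains in every case.

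The planned Part A draw for a 50 kg patient is about 5.1% of blood volume at visit 2 and 7.5% at visit 3, 13.4% over the study, assuming 70 mL/kg. A reader might infer that a recent HD donor would lose 26 to 28% of blood volume. That is only a cumulative upper bound. It adds a full donation to every sample over four visits, allows no replacement, and takes the minimum weight. Nor do the documents support calling the HD patients frailer: they must be ambulatory.

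The 467.8 mL is the planned total. The protocol does not say whether late arterial samples are dropped when an HD patient skips the later PET blocks. A repeated postdose PET with full arterial resampling (assumed) would add 166 mL.

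Severity is minor, given an optional cohort of up to 4 patients and the existing laboratory checks.

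**What to change.** Reconcile the HD exclusion list in Section 4.2 with healthy criterion v, at least for Part A, or state in Section 4.3 why the two populations differ. Make the matching edit in the synopsis. Section 5.2 needs no change, because its donation bullets already agree.

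The cost is one line in Section 4.2 and one in the synopsis, or one sentence of justification. It needs no new procedure or sample, and the effect on recruiting up to 4 patients should be negligible.

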5.3. Prior and Concomitant Medication or Treatment

Medications administered prior to any study drug administration will be recorded as prior medications and medications administered following the first dose and throughout the study will be recorded as concomitant medication. Any prior or concomitant therapy, medication, or procedure a subject has had within 28 days before study drug administration and up to the end of the study period, including follow-up, will be recorded on the CRF. Generic or trade name, indication, dosage, and dosing start and stop times will be recorded. The sponsor will encode all therapy and medication according to the World Health Organization drug dictionary (WHO Drug).

For healthy subjects, other than study drug, no drug is allowed during the study, except for the occasional use of paracetamol/acetaminophen or ibuprofen. Prohibited medication for HD patients is detailed in Section 5.3.1.

At each clinic visit after the screening visit, the investigator will ask subjects whether they have taken any medications (other than study drug), including OTC medications, vitamins, or herbal or nutritional supplements, since the previous visit. Indication, dosage, and start and end dates should be entered on the CRF.

5.3.1. Prohibited Medication for HD Patients

5.3.1.1. Antipsychotic Medication

Ziprasidone, clozapine, haloperidol, mesoridazine, thioridazine, pimozide, zuclopentixol, chlorpromazine, paliperidone, iloperidone, fluphenazine, prochlorperazine, trifluoperazine/trifluoperazine, flupentixol, benperidol, amisulpride, and sulpiride are not allowed within 6 weeks of baseline (visit 2, day -1) and during the study.

5.3.1.2. Antidepressant Medication

Lithium, the tricyclic/tetracyclic antidepressants trazodone, amitriptyline, nortriptyline, imipramine, desipramine, maprotiline, doxepin, clomipramine, protriptyline, and amoxapine, and the serotonin–norepinephrine reuptake inhibitors citalopram, escitalopram, and fluoxetine are not allowed within 6 weeks of baseline (visit 2, day -1) and during the study.

5.3.1.3. Antiarrhythmic Medication

Disopyramide, procainamide, quinidine, flecainide, propafenone, amiodarone, dofetilide, ibutilide, and sotalol are not allowed within 6 weeks of baseline (visit 2, day -1) and during the study.

5.3.1.4. Medications Lowering Seizure Thresholds

Maprotiline, dipipanone, dihydrocodeine, methadone, oxycodone, papaveretum, pentazocine, and tramadol are not allowed within 6 weeks of baseline (visit 2, day -1) and during the study

5.3.1.5. Medications Interfering with Blood Coagulation

The following medications are not allowed within 6 weeks of baseline (visit 2, day -1) and during the study (except if required to treat adverse events):

- Drugs which inhibit platelet function (antithrombic drugs) – aspirin, dipyridamole, sulfinpyrazone, dextran
- Drugs which decrease fibrin formation (anticoagulants) - heparin, oral anticoagulants: coumarin (warfarin, bishydroxycoumarin) and indandione (phenindione) derivatives.
- thrombolytic drugs: streptokinase, urokinase, tissue plasminogen activator
- Miscellaneous drugs which are used to affect hemostasis: aminocaproic acid; tranexamic acid; desmopressin; dihydroergotamine mesylate; pentoxifyllin.

